### 15.6.1 Relationship of QTc Changes to Treatment Exposure

A secondary objective of the protocol was to assess QT prolongation potential by central tendency, outlier analysis and the slope of exposure-QTc analysis. Time-matched ECG readings (3 or more replicates) were to be collected at -45, -30, and -15 minutes predose and at 0.5, 1, 2, 3, 4, 6, and 8 hours postdose, just prior to PK sample collections during Cycle 1 at Day 1 and Day 15 during Part IA (M4112 monotherapy) and uploaded for central ECG reading. ECG readings collected on Cycle 1 Day 8 (predose) and Cycle 2 Day 1 (predose and 2 hours postdose) were also to be uploaded. As the study was terminated early, the following analyses are planned to address the potential relationship of QTc changes to the plasma M4112 exposure, based on the Concentration-QTc Analysis Set:

- The average QTc value at each time point will be plotted for each planned dose level for C1D1, C1D8, C1D15 and C2D1.

- The change from baseline will be calculated as the mean change in QTc at each time point (including C1D1, C1D8, C1D15 and C2D1) minus the mean of 3 predose time points (-45, -30 and -15 minutes) on C1D1 and plotted for each time point (if possible, these will be plotted in a joint plot – change in QTc on the left axis and M4112 plasma concentration on the right axis with time on the x-axis).
- The change from baseline for each time-matched sample will be plotted against the corresponding M4112 plasma concentration for all days and all planned dose levels (combined and separately) in a scatter plot.

Because the data is limited, no linear modeling will be applied.

## 15.7 ECOG Performance Status

The ECOG shift from baseline to highest score during the on-treatment period will be summarized. ECOG performance status with shift from ECOG = 0 or 1 to ECOG = 2 or higher will also be presented in a data listing with subject identifier and other relevant information.

## 16 Analyses of Other Endpoints

### 16.1 Pharmacokinetics

#### 16.1.1 Plasma Concentrations

##### M4112 Concentrations

All descriptive summaries of M4112 plasma concentrations will be performed on the PK Analysis Set. Any concentrations excluded from the PK Analysis Set will be listed and flagged.

Pharmacokinetic concentrations will be reported and analyzed with the same precision as the source data provided by the bioanalytical laboratory or clinical laboratory. Actual elapsed sample collection times will be analyzed unrounded (maximum of 14 significant digits), but will be rounded to two decimal places with units of hours for reporting purposes in by-subject listings.

Predose samples that occur before drug administration will be assigned a time of 0 hours, as if the sample had been taken simultaneously with the study drug administration.

Concentration values below the lower limit of quantification of the assay (LLOQ) will be taken as zero for summary statistics of PK concentration data.

In case of concentrations above the upper limit of quantification of the assay (ULOQ), the concentration will be set to missing.

Missing concentrations (e.g., no sample, insufficient sample volume for analysis, no result, or result not valid) will be reported and used generally as no result ("NR").

[figure not shown]
M4112 plasma concentration data will be descriptively summarized by study day and nominal time using: number of subjects (N), number of nonmissing values (n), arithmetic mean (Mean), standard deviation, coefficient of variation (CV%), minimum (Min), Median, and maximum (Max). If N is less than 3, only n, Min, and Max will be presented.

Descriptive statistics of plasma concentration data will be calculated using values with the same precision as the source data, and rounded for reporting purposes only. The following conventions will be applied when reporting descriptive statistics for concentrations:

Mean, Min, Median, Max:	3 significant digits
Standard Deviation:	4 significant digits
CV%:	1 decimal place

Individual concentration-time profiles showing all subjects separately by dose group and study day (C1D1 and C1D15), and showing study days (C1D1 and C1D15) separately by subject will be created using the actual time points and the numeric concentration data. Arithmetic mean concentration-time profiles by dose group separately for each study day (C1D1 and C1D15), and by study day (C1D1 and C1D15) separately for each dose group will be provided using scheduled (nominal) time points and the numeric concentration data. All concentration-time plots for PK data will be presented both on a linear and on a semi-logarithmic scale. Mean plots will include standard deviation bars when plotted on a linear scale.

CCI

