## 8.2 Definition of Analysis Sets and Subgroups

The analysis sets of subjects whose data will be included in the analyses described in this IAP are defined in [Table 1](#).

**Table 1** Analysis Sets

Population	Description
Screening (SCR)	All subjects who sign informed consent.
DLT	All subjects who received at least one dose of study intervention and meet at least one of the following criteria: 

- Received at least 5 planned cumulative total daily doses of M4112 in the first cycle (first 28 days) or

- Experienced at least one DLT during the DLT period, regardless of the administered number of doses of study intervention/completion of the DLT period

Safety	The Safety Analysis Set will include all subjects who receive at least 1 dose of study treatment.
Concentration-QTc Analysis Set	The cQTc Analysis Set will include all subjects with at least baseline and one on treatment measurement of time-matched ECG and M4112 plasma concentration collected during the dose-escalation phase.
M4112 Pharmacokinetic	All subjects from the Safety Analysis Set without clinically important protocol deviations/violations or events that would affect PK (see Section 8.1 ). Subjects in the PK Analysis Set must have received at least 1 dose of M4112 and must have sufficient M4112 plasma concentration data to enable the calculation of at least 1 PK parameter. Sufficient concentration data is defined as at least 3 valid, postdose concentration points in the PK profile to obtain any PK parameter.
Pharmacodynamics	All subjects who received at least 1 dose of M4112 and provide the predose and at least 1 postdose sample for Pd assessment.

cQTc = concentration-QTc response; DLT = dose-limiting toxicities; ECG = electrocardiogram;

Pd = pharmacodynamics; PK = pharmacokinetic; QTc = corrected QT interval.

There are no subgroup analyses planned for this study.

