### 16.1.2 Plasma Pharmacokinetic Parameters

Pharmacokinetic parameters will be calculated using standard noncompartmental methods and the actual administered dose. Pharmacokinetic parameters will be calculated using the actual elapsed time since dosing, given with a precision of 14 significant digits. In cases where the actual sampling time is missing, calculations will be performed using the nominal time. Otherwise, there will be no further imputation of missing data.

The following parameters will be calculated from M4112 plasma concentrations on the study days specified.

Symbol	Definition
AUC 0-8	The area under the concentration-time curve (AUC) from time zero (= dosing time) to 8 hours postdose, calculated on C1D1 and C1D15. Calculated using the mixed log linear trapezoidal rule (linear up, log down).
AUC 0-8 /Dose	The dose-normalized AUC 0-8 , calculated on C1D1 and C1D15. Normalized using the actual dose, using the formula AUC 0-8 /Dose.
C max	Maximum observed concentration, calculated on C1D1 and C1D15.
C max /Dose	The dose-normalized C max , calculated on C1D1 and C1D15. Normalized using the actual dose, and the formula C max /Dose.
t max	The time to reach the maximum observed concentration (in case of multiple/identical C max values, the first occurrence will be used), calculated on C1D1 and C1D15.
C pre	Predose (trough) observed concentration, calculated on C1D8, C1D15, and C2D1.
C pre /Dose	The dose-normalized C pre , calculated on C1D8, C1D15, and C2D1. Normalized using the actual dose, and the formula C pre /Dose.
R acc (AUC 0-8 )	The accumulation factor to assess the increase in exposure via AUC 0-8 following multiple dosing. R acc (AUC 0-8 ) = (AUC 0-8 after multiple dose [C1D15]) / (AUC 0-8 after single dose [C1D1]).
R acc (C max )	The accumulation factor to assess the increase in maximum concentration following multiple dosing. R acc (C max ) = (C max after multiple dose [C1D15]) / (C max after single dose [C1D1]).

For all dose-normalized parameters, no adjustment of dose (e.g., for molecular weight differences between salt and free form) is required as M4112 is not a salt.

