Individual  $C_{pre}$  values on C1D8, C1D15, and C2D1 will be plotted against actual time points (in days) on a linear scale, for all subjects by dose group. Arithmetic mean  $C_{pre}$  (with standard deviation bars) will also be plotted versus nominal time (in days) by dose group, on a linear scale.

The analysis of dose proportionality of PK parameters of M4112 over the range of administered dose levels will be quantified as part of an exploratory analysis using the power model on the original parameters ( $\ln[\text{PK parameter}] = \alpha + \beta \times \ln[\text{dose}]$ ). This analysis will be based on  $AUC_{0-8}$  (C1D1 and C1D15),  $C_{max}$  (C1D1 and C1D15), and  $C_{pre}$  (C1D8, C1D15, C2D1) and will be conducted separately by parameter and study day. The intercept  $\alpha$  and the slope  $\beta$  together with 90% CIs will be estimated and presented. A p-value testing whether  $\beta = 1$  will also be presented. For a given parameter, a minimum of 3 values must be available for a dose level, for that dose level to be included in the dose proportionality analysis.

Dose proportionality will also be assessed graphically by presenting scatter plots of individual and geometric mean values of  $AUC_{0-8}$  (C1D1 and C1D15),  $C_{max}$  (C1D1 and C1D15), and  $C_{pre}$  (C1D8, C1D15, C2D1) and dose-normalized  $AUC_{0-8}$  (C1D1 and C1D15),  $C_{max}$  (C1D1 and C1D15), and  $C_{pre}$  (C1D8, C1D15, C2D1) versus Dose on a linear scale. Plots will be prepared separately by PK parameter and study day.

CCI

CCI

[REDACTED]

[REDACTED]

[REDACTED]

[REDACTED]

[figure not shown]
[REDACTED]

[REDACTED]

CCI

[REDACTED]

[REDACTED]

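### Setting concentrations above the assay's upper limit to missing would understate Cmax and AUC0-8 at high exposure and pull the dose-proportionality slope below its true value, if any final result stays above that limit

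*SAP*

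**What the plan says.** IAP 16.1.1 (M4112 Concentrations) gives the rule: "In case of concentrations above the upper limit of quantification of the assay (ULOQ), the concentration will be set to missing". Missing concentrations "will be reported and used generally as no result" (NR). Low values are handled differently: "Concentration values below the lower limit of quantification of the assay (LLOQ) will be taken as zero for summary statistics of PK concentration data".

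IAP 16.1.2 then derives the parameters by noncompartmental methods. A missing actual time is replaced by the nominal time. "Otherwise, there will be no further imputation of missing data". Cmax is the "Maximum observed concentration, calculated on C1D1 and C1D15", tmax is its time, and AUC0-8 uses the linear-up, log-down trapezoidal rule. IAP 8.2 sets the entry condition: "Sufficient concentration data is defined as at least 3 valid, postdose concentration points in the PK profile to obtain any PK parameter".

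On the final use, IAP 16.1.2 says: "The analysis of dose proportionality of PK parameters of M4112 over the range of administered dose levels will be quantified". The method is a power model, ln(parameter) on ln(dose), with 90% confidence intervals and a p-value for a slope of 1. A dose level needs at least three values to enter.

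Protocol 8.5.4 has a rule for values below the lower limit of quantification but none for values above the upper one. Neither document states the ULOQ or a dilution rule; Protocol 7.5 refers to a separate bioanalytical report.

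**The concern.** A lost tube carries no information about its concentration. A result above ULOQ does: the concentration was at least ULOQ. The rule treats the two alike. Because deletion is triggered by the value being high, it takes only the top of a profile, and it acts more often at high doses and in high-exposure subjects.

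Reported Cmax can then never exceed ULOQ. Section 16.1.2 sets AUC0-8 to missing when the 8-hour sample is more than 10 minutes early, but has no matching provision for a deleted peak, which can do more damage.

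Cmax, AUC0-8, their dose-normalised values and the accumulation ratios are secondary endpoints. The protocol calls M4112 a sensitive CYP3A4 substrate and cannot exclude that it inhibits or induces that enzyme (Protocol 3.4.2.1). More-than-proportional exposure would therefore be a finding of interest, and this rule tends to hide it. The same deletion may also thin the high-concentration end of the concentration-QTc scatter plots (IAP 15.6.1), which replace the dropped slope analysis.

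**Working it through.** The plan gives no figure on this point to reproduce. The check asks what the written rules produce when a peak exceeds ULOQ.

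**Inputs from the documents.** Samples predose and at 0.5, 1, 2, 3, 4, 6 and 8 h; doses 100, 200, 400, 600, 800 and 900 mg; the planning scenario in Protocol 8.1, 4 × 3 + 2 × 6 = 24 subjects; the AUC rule, the three-postdose-point rule, the power model and its three-values-per-level rule.

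**Assumed, because not given.** A one-compartment oral profile, C(t) ∝ ka/(ka − ke) × [exp(−ke·t) − exp(−ka·t)], with ke = ln 2/half-life, absorption rate ka 1-2 per h and half-life 3-6 h. Peak means the highest sampled value.

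**One profile by hand** (ka 1 per h, half-life 4 h, peak 1.25 × ULOQ, so ULOQ = 1/1.25 = 0.80 of the peak):

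| h | 0 | 0.5 | 1 | 2 | 3 | 4 | 6 | 8 |
|---|---|---|---|---|---|---|---|---|
| C/peak | 0 | 0.543 | 0.827 | 1 | 0.953 | 0.842 | 0.614 | 0.437 |
| Kept | yes | yes | no | no | no | no | yes | yes |

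- Three postdose points remain, so the profile is still analysed.
- Cmax = 0.614, or 61% of true. tmax moves from 2 h to 6 h.
- True AUC0-8 = 0.136 + 0.343 + 0.914 + 0.976 + 0.896 + 1.444 + 1.041 = 5.75.
- AUC0-8 under the rule = 0.136 + 5.5 × (0.543 + 0.614)/2 + 1.041 = 0.136 + 3.182 + 1.041 = 4.36. Ratio 4.36/5.75 = 76%.

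**The grid** (ka 1, 1.5, 2 per h; half-life 3, 4, 6 h; nine profiles).

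- Peak at 1.25 × ULOQ: 2-4 samples are deleted and 3-5 postdose points remain. Cmax is 61-79% and AUC0-8 76-93% of true. tmax can also move early: with ka 2 per h and half-life 3 h it goes from 1 h to 0.5 h.
- Peak at 1.5 × ULOQ: six of the nine profiles keep only two postdose points and yield no parameters under IAP 8.2. The highest exposures are then lost rather than understated.

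**Dose-proportionality slope.** Simulated trials with a true slope of 1, 24 subjects (six each at 800 and 900 mg, an assumption), between-subject SD 0.4 on the log scale, ka 1.5 per h, half-life 4 h, and the IAP's own inclusion rules. The mean Cmax slope is 1.00 without deletion.

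| ULOQ equal to the typical peak at | Mean Cmax slope, rule as written |
|---|---|
| 900 mg | about 0.91 |
| 700 mg | about 0.83 |
| 500 mg | about 0.78 |

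A second simulation (ka 1.2 per h, ke 0.25 per h, between-subject CV 30% or 50%, 10% residual error) agrees. With ULOQ at 0.9 times the typical 900 mg peak the mean Cmax slope is 0.87 or 0.83; at 1.2 times, 0.96 or 0.91; at 2 times, about 0.99; at 5 times, 1.00.

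**Simple alternatives.** Withholding parameters for every affected profile gives a mean Cmax slope of about 0.87 with ULOQ at the 900 mg peak (0.91 under the rule as written) and about 0.87 at the 700 mg peak (0.83 as written). Substituting ULOQ for the deleted values, in the second simulation with ULOQ at 0.9 times the 900 mg peak, gives 0.91 or 0.88, and pulls mean tmax early (about 1.4 or 1.3 h against 1.8 h). Only the true re-assayed values restore 1.00.

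**The case against.** The strongest reply is that the rule may never act. Dilution and re-assay are normally settled in the bioanalytical method, which Protocol 7.5 places in a separate report. The sentence may only be a backstop for samples with no valid result. This stands, and it makes every figure above conditional. A reader might infer that the final results are biased; the documents do not show that any sample exceeded ULOQ.

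Second, IAP 8.1 lets the PK scientist judge events affecting PK case by case, names incomplete data among them, and allows exclusion with sponsor agreement; exclusions are listed and flagged. The route exists, but it is discretionary and has no ULOQ criterion, so it does not correct the written rule.

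Third, a reader might infer that affected profiles are always analysed with a low Cmax. At 1.5 × ULOQ most drop out instead, and a level with fewer than three values leaves the power model.

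Fourth, a reader might infer an effect on dose escalation. The analysis plan for the Safety Monitoring Committee (its section 16.2.1) has no ULOQ rule, and this IAP covers only the abbreviated final analysis, which is descriptive, with an exploratory power model. No effect on escalation is shown.

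Fifth, the rule sits in the PK section, while the QTc plots use their own analysis set, so carry-over there is an inference. The direction for the accumulation ratios is also open, since either day can lose points.

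**Conclusion.** The point holds as a conditional defect in a prespecified rule. Whenever a final result stays above ULOQ at the peak, the rules as written either understate Cmax and AUC0-8 or remove the profile, and tmax becomes unreliable. With the peak at 1.25 × ULOQ and the assumed profiles, Cmax is about 61-79% and AUC0-8 about 76-93% of true. For a proportional drug the mean Cmax slope is about 0.91 or 0.83 with ULOQ at the typical 900 or 700 mg peak. With ULOQ well above the observed range the effect is nil. These figures rest on an unstated ULOQ, assumed kinetics and dosing up to 900 mg; the IAP does not say which doses were given.

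The slope is pulled below its true value, which need not mean below 1: a more-than-proportional drug could look proportional. The primary endpoints are untouched. The change should still be made, because it is cheap and the present rule gives a wrong answer whenever it acts.

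**What to change.** Replace the sentence in IAP 16.1.1 with:

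*Samples above ULOQ are diluted and re-assayed within the validated dilution range and the diluted result is used. If no valid result can be obtained, the value is listed as >ULOQ; Cmax for that profile is reported as a lower bound (at least ULOQ), and tmax and AUC0-8 are flagged as not reliably estimable and left out of the summary statistics. The number of such profiles is shown by dose level. The dose-proportionality model treats the affected Cmax values as right-censored at ULOQ, and neither deletes them nor uses the next-highest sample.*

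The same flag should carry through to the dose-normalised values and accumulation ratios built on these parameters.

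The cost is a few sentences, possibly a re-assay of existing plasma, and a little more analysis work. Whether usable plasma remains is unknown, since Protocol 7.5 allows leftovers to be used for metabolites. Without re-assay, leaving out AUC0-8 for affected profiles is still value-dependent missingness; the counts by dose level let a reader see how much is lost and where. If the laboratory already dilutes, the edit only records that practice.

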### 16.1.2 Plasma Pharmacokinetic Parameters

Pharmacokinetic parameters will be calculated using standard noncompartmental methods and the actual administered dose. Pharmacokinetic parameters will be calculated using the actual elapsed time since dosing, given with a precision of 14 significant digits. In cases where the actual sampling time is missing, calculations will be performed using the nominal time. Otherwise, there will be no further imputation of missing data.

The following parameters will be calculated from M4112 plasma concentrations on the study days specified.

Symbol	Definition
AUC 0-8	The area under the concentration-time curve (AUC) from time zero (= dosing time) to 8 hours postdose, calculated on C1D1 and C1D15. Calculated using the mixed log linear trapezoidal rule (linear up, log down).
AUC 0-8 /Dose	The dose-normalized AUC 0-8 , calculated on C1D1 and C1D15. Normalized using the actual dose, using the formula AUC 0-8 /Dose.
C max	Maximum observed concentration, calculated on C1D1 and C1D15.
C max /Dose	The dose-normalized C max , calculated on C1D1 and C1D15. Normalized using the actual dose, and the formula C max /Dose.
t max	The time to reach the maximum observed concentration (in case of multiple/identical C max values, the first occurrence will be used), calculated on C1D1 and C1D15.
C pre	Predose (trough) observed concentration, calculated on C1D8, C1D15, and C2D1.
C pre /Dose	The dose-normalized C pre , calculated on C1D8, C1D15, and C2D1. Normalized using the actual dose, and the formula C pre /Dose.
R acc (AUC 0-8 )	The accumulation factor to assess the increase in exposure via AUC 0-8 following multiple dosing. R acc (AUC 0-8 ) = (AUC 0-8 after multiple dose [C1D15]) / (AUC 0-8 after single dose [C1D1]).
R acc (C max )	The accumulation factor to assess the increase in maximum concentration following multiple dosing. R acc (C max ) = (C max after multiple dose [C1D15]) / (C max after single dose [C1D1]).

For all dose-normalized parameters, no adjustment of dose (e.g., for molecular weight differences between salt and free form) is required as M4112 is not a salt.

Partial area (AUC0-8) will be calculated using the nominal dosing interval if the PK sample at 8 hours postdose is taken at  $\geq$ 8 hours. If the 8-hour sample is taken earlier than 8 hours, then the actual time and concentration at the nominal 8-hour time point will be used to calculate this parameter as long as the time deviation at 8 hours is not  $>10$  min (ie, the protocol-allowed window at this time point); otherwise this parameter will be set to missing.

Concentrations below the LLOQ at any point in the profile will be taken as zero for calculating AUC. Predose samples that occur before the first drug administration will be assigned a time of 0 hours, as if the sample had been taken simultaneously with the study drug administration.

The Phoenix WinNonlin NCA Core Output will be provided in a separate listing.

All statistical analyses and descriptive summaries of PK parameters will be performed on the PK Analysis Set. Any PK parameters excluded from the PK Analysis Set will be listed and flagged.

Pharmacokinetic parameters will be analyzed unrounded, but will be rounded to 3 significant digits for reporting, except for parameters directly obtained from the source data (such as  $C_{max}$ ) which will be reported with the same precision as the source data, and  $t_{max}$  which will be reported to 2 decimal places. In export datasets, as well as in the SDTM PP/XD domain, PK parameters will be provided with full precision, and will not be rounded.

Calculated PK parameters will be descriptively summarized by study day using: N, n, Mean, standard deviation, CV%, Min, Median, Max, geometric mean (GeoMean), and geometric coefficient of variation (GeoCV%). GeoMean and GeoCV% will not be presented for  $t_{max}$ . If N is less than 3, only n, Min, and Max will be presented.

Descriptive statistics of PK parameter data will be calculated using full precision values, and rounded for reporting purposes only.

The following conventions will be applied when reporting descriptive statistics of PK parameter data, except for  $t_{max}$  which will use the same level of decimal precision (instead of significant digits) as specified below:

Mean, Min, Median, Max, GeoMean:	3 significant digits
Standard Deviation:	4 significant digits
CV%, GeoCV%:	1 decimal place

Individual  $C_{pre}$  values on C1D8, C1D15, and C2D1 will be plotted against actual time points (in days) on a linear scale, for all subjects by dose group. Arithmetic mean  $C_{pre}$  (with standard deviation bars) will also be plotted versus nominal time (in days) by dose group, on a linear scale.

The analysis of dose proportionality of PK parameters of M4112 over the range of administered dose levels will be quantified as part of an exploratory analysis using the power model on the original parameters ( $\ln[\text{PK parameter}] = \alpha + \beta \times \ln[\text{dose}]$ ). This analysis will be based on  $AUC_{0-8}$  (C1D1 and C1D15),  $C_{max}$  (C1D1 and C1D15), and  $C_{pre}$  (C1D8, C1D15, C2D1) and will be conducted separately by parameter and study day. The intercept  $\alpha$  and the slope  $\beta$  together with 90% CIs will be estimated and presented. A p-value testing whether  $\beta = 1$  will also be presented. For a given parameter, a minimum of 3 values must be available for a dose level, for that dose level to be included in the dose proportionality analysis.

Dose proportionality will also be assessed graphically by presenting scatter plots of individual and geometric mean values of  $AUC_{0-8}$  (C1D1 and C1D15),  $C_{max}$  (C1D1 and C1D15), and  $C_{pre}$  (C1D8, C1D15, C2D1) and dose-normalized  $AUC_{0-8}$  (C1D1 and C1D15),  $C_{max}$  (C1D1 and C1D15), and  $C_{pre}$  (C1D8, C1D15, C2D1) versus Dose on a linear scale. Plots will be prepared separately by PK parameter and study day.

CCI

CCI

[REDACTED]

[REDACTED]

[REDACTED]

[REDACTED]

[figure not shown]
[REDACTED]

[REDACTED]

CCI

[REDACTED]

[REDACTED]

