### 6.2.1 Dose Escalation Cohort (Part I)

#### 6.2.1.1 Subjects Receiving M4112 as Single Agent

##### Administration of M4112:

BID continuous administration of M4112 as single agent at doses recommended by the SMC is foreseen. On study site visit days, the morning dose of M4112 will be taken at the study site.

CCI [REDACTED]

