### 7.5.2            Pharmacokinetic Calculations

The software to be used and PK calculations and parameters will be specified in the integrated analysis plan (iAP).

For M4112, PK calculations using standard noncompartmental analysis methods will be performed, if appropriate, using commercial software such as Phoenix® WinNonlin® (Version 6.3 or higher) at **PPD** by standard methods. Actual dates and times as recorded on the eCRF will be utilized for final analyses, however, nominal times may be used for PK determinations in support of the SMC review (See Section 8.6).

All other data handling procedures will be detailed in the iAP.

Pharmacokinetic parameters to be calculated for M4112 are specified in Table 11.

**Table 11** Pharmacokinetic Parameters for M4112

AUC 0-8	Area under the plasma concentration-time curve from time zero to 8 h postdose
C max	Maximum plasma concentration observed postdose
t max	Time to reach maximum plasma concentration
C min	Minimum observed postdose (trough) plasma concentration
AUC 0-8/dose	Area under the plasma concentration-time curve from time zero to 8 h postdose/dose
C max/dose	Maximum observed plasma concentration/dose
C min/dose	Minimum observed postdose (trough) plasma concentration/dose
R acc (AUC 0-8 )	Accumulation of the M4112 AUC 0-8 (Day 15/Day 1)
R acc (C max )	Accumulation of the M4112 C max (Day 15/Day 1)

Final PK parameters reported will be detailed in the iAP.

A population pharmacokinetic (PopPK) model will be constructed to allow for calculation of PopPK parameters for M4112 and the analysis of selected covariates. PopPK analyses will be detailed in a separate analysis plan.

Serum concentrations for **CCI** will be summarized and may be included in population PK analyses models constructed for each analyte, respectively.

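### The SAP's AUC0-8 rule sets the upper limit at the dosing interval (about 12 h under BID) where the parameter's definition says 8 h; a minor wording error that should be corrected

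*SAP*

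**What the plan says.** The SAP (titled Integrated Analysis Plan) defines AUC0-8 in the parameter table of section 16.1.2 as "The area under the concentration-time curve (AUC) from time zero (= dosing time) to 8 hours postdose, calculated on C1D1 and C1D15". Protocol 7.5.2, Table 11, agrees: "Area under the plasma concentration-time curve from time zero to 8 h postdose".

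The text below the SAP table says how the upper limit is handled when the last sample is not drawn at exactly 8 h:

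- **Sample at or after 8 h.** The area "will be calculated using the nominal dosing interval if the PK sample at 8 hours postdose is taken at" that time or later.
- **Sample up to 10 minutes early.** If the sample is before 8 h, "then the actual time and concentration at the nominal 8-hour time point will be used to calculate this parameter".
- **Sample more than 10 minutes early.** The parameter is set to missing.

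On the regimen, Protocol 6.2.1.1 states: "BID continuous administration of M4112 as single agent at doses recommended by the SMC is foreseen". Protocol Table 4, footnote d, places the predose sample about 12 h (± 4 h) after the last evening dose. Protocol 6.2 also lets the Safety Monitoring Committee change the regimen, for example to once daily. Profile sampling on Days 1 and 15 of Cycle 1 ends at 8 h (Protocol Table 4).

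**The concern.** The first branch names an upper limit that is not 8 h. Under twice-daily dosing the nominal interval is about 12 h, and under a once-daily regimen it would be 24 h. The second branch stops just short of 8 h. Taken at its word, the rule attaches one parameter name to areas over different time spans, and a few minutes of sampling time decide which one a subject gets.

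The phrase is not a local synonym for 8 h. Elsewhere the SAP uses it for the time between doses: section 7 warns that the predose concentration may not reflect the true value at the end of the dosing interval, and section 8.1 discusses inaccurate dosing intervals before a PK dose.

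AUC0-8 is a secondary endpoint (SAP 5.1). It feeds AUC0-8/Dose, the accumulation ratio Racc(AUC0-8) and the dose-proportionality power model. Cohorts are usually 3 subjects, so a single value on a different time span would visibly move a cohort mean.

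**Working it through.** The plan states no AUC figure, so there is nothing to reproduce. The check has a textual part and an illustration of size.

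**1. The upper limit in each place**

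| Place | Upper limit |
|---|---|
| SAP 16.1.2, parameter table | 8 h |
| Protocol 7.5.2, Table 11 | 8 h |
| SAP 16.1.2, sample at or after 8 h | nominal dosing interval, about 12 h under BID |
| SAP 16.1.2, sample up to 10 min early | actual time, 7 h 50 min to just under 8 h |

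The third row conflicts with the other three.

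**2. Can a 12-h area be computed as specified?** The last profile sample is at 8 h. The SAP parameter list has no terminal rate constant or half-life, and no extrapolation rule is given. Section 16.1.2 allows the nominal time to stand in for a missing sampling time and rules out any further imputation. An analyst would have to supply a method for 8 to 12 h.

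**3. Size if 12 h were used.** These are assumptions, because the documents give neither parameter: one-compartment oral kinetics, half-life 3, 4, 6, 8 or 12 h, ka 0.7 or 1.5 per h, ke = ln 2 / half-life. Up to a constant, for a single dose:

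AUC(0,T) = ka/(ka − ke) × [(1 − e^(−ke·T))/ke − (1 − e^(−ka·T))/ka]

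At 12-h steady state, the first term in the brackets is divided by (1 − e^(−12·ke)) and the second by (1 − e^(−12·ka)). The two extremes of the grid are:

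| Case | AUC0-8 | AUC0-12 | Ratio |
|---|---|---|---|
| Day 1, half-life 3 h, ka 1.5 | 3.522 | 4.008 | 1.138 |
| Day 1, half-life 12 h, ka 0.7 | 5.431 | 7.878 | 1.451 |
| Steady state, half-life 3 h, ka 1.5 | 3.810 | 4.328 | 1.136 |
| Steady state, half-life 12 h, ka 0.7 | 12.413 | 17.312 | 1.395 |

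The other grid points lie between these. A separate calculation used linear-up/log-down areas on the protocol sampling times, extrapolation from the last three points, and half-lives from 2 to 12 h. It gave 1.07 to 1.47. A flat curve gives 12/8 = 1.5.

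**4. What this does downstream**

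- AUC0-8/Dose is multiplied by the same ratio.
- Racc(AUC0-8) is Day 15 over Day 1. If only Day 15 used 12 h, it is multiplied by 1.14 to 1.40. If only Day 1 did, it is multiplied by 1/1.451 = 0.69 to 1/1.138 = 0.88. If both did, the factors nearly cancel: 1.395/1.451 = 0.96 to 1.136/1.138 = 1.00.
- In the power model, an affected value moves on the log scale by ln 1.14 = 0.13 to ln 1.45 = 0.37. A shift common to all subjects would leave the slope unchanged; a mixture would not.

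**5. Size with an 8-h limit.** For a sample 10 minutes early, AUC(0, 7.833 h)/AUC(0, 8 h) on Day 1 is 5.317/5.431 = 0.979 at one extreme and 3.491/3.522 = 0.991 at the other. The flat-curve value is 7.833/8 = 0.979. The branches then differ by at most about 2%.

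**The case against.** The strongest reply is that the documents already settle the limit. The rule is stated for a parameter named AUC0-8, which the SAP table and the protocol both define as ending at 8 h. Asking whether the sample is at or after 8 h makes sense only if 8 h is the target, because interpolation to 8.00 h is then possible; with a 12-h target, a sample at 8:05 falls short as well. A 12-h area would need an extrapolation that the SAP does not provide. All analyses are descriptive, dose proportionality is labelled exploratory, and the WinNonlin core output is listed, so a departure from 0-8 h could be seen.

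All of this stands as evidence of intent, and it keeps the point minor. It does not make the sentence correct. That sentence is the only instruction for a sample drawn at or after 8 h, and the SAP nowhere says to truncate or interpolate at 8.00 h. The programmer has to override a written rule to reach the right area.

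A reader might go further and infer that reported cohorts will contain a mixture of 12-h and 8-h areas. The documents do not support that: it happens only if the sentence is applied against the parameter's own definition, with an invented method for the last 4 hours. Nor do they support any estimate of how many subjects would have Day 1 and Day 15 in different branches, because nothing is said about the distribution of sampling times or their independence between days. A reader might also infer that a drug with no accumulation would appear to accumulate. The model used above cannot show that case: its own Racc(AUC0-8) runs from 1.08 to 2.29 over the grid, so the Racc factors should be read only as multipliers.

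**Conclusion.** The point holds as a minor inconsistency. The rule for samples at or after 8 h names the dosing interval, about 12 h under BID, and so contradicts the 0-8 h definition in the same section and in the protocol. The intended limit is almost certainly 8 h.

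If the rule were applied literally, the affected areas would be about 1.14 to 1.45 times the 0-8 h area. That range depends entirely on the assumed one-compartment profiles and on a 12-h extrapolation that the SAP does not specify. If 8 h is used, what remains is a difference of at most about 2% between the branches, which needs no further action.

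**What to change.** In SAP 16.1.2, in the rule for samples at or after 8 h, replace *the nominal dosing interval* with *the nominal time of 8 hours postdose (area truncated at 8.00 h by interpolation)*. The early-sample branch and the 10-minute limit can stay as they are.

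The cost is one phrase in the SAP. No new data, assay or design change is needed, and the wording would remain correct if the regimen changed.
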